### **AEs that are considered “Dose Limiting” for talimogene laherparepvec**

- 1) Herpetic events that should be considered DLTs:
  - Serious herpetic events such as herpetic encephalitis, encephalomyelitis or disseminated herpetic infection

- Any herpetic events confirmed due to talimogene laherparepvec that require treatment with acyclovir or similar anti-viral agent. Talimogene laherparepvec treatment should be held if systemic acyclovir or other anti-viral is indicated. If ongoing anti-viral treatment is required, talimogene laherparepvec treatment should be permanently discontinued
  - \* Herpetic events due to wild-type HSV-1 or wild-type HSV-2 which require acyclovir and are not due to talimogene laherparepvec (as confirmed by PCR testing) should not be considered as DLTs caused by talimogene laherparepvec.

2) DLT will also be defined as any of the following talimogene laherparepvec-related toxicity:

- Grade 2 or greater immune-mediated AEs.
- Grade 2 or greater allergic reactions.
- Any grade plasmacytoma
- Any other grade 3 or greater hematologic or non-hematologic toxicity, with the exceptions of:
  - any grade of alopecia,
  - grade 3 arthralgia or myalgia,
  - brief (< 1 week) grade 3 fatigue,
  - grade 3 fever,
  - grade 3 diarrhea or vomiting responding to supportive care.

For other study treatments, DLT will be defined as clinically significant (ie excluding any grade alopecia, grade 3 arthralgia or myalgia, < 1 week grade 3 fatigue, grade 3 diarrhea, nausea, vomiting responding to supportive care), grade 3 or 4 toxicities possibly or probably related to study treatment or AEs.

Management and dose modifications associated with the above adverse events are outlined in Section 6.

Dose escalation will proceed within each cohort according to the following scheme. Dose-limiting toxicity (DLT) is defined above.

Number of Patients with DLT at a Given Dose Level	Escalation Decision Rule
0 out of 3	Enter 3 patients at the next dose level.
≥2	Dose escalation will be stopped. This dose level will be declared the maximally administered dose (highest dose administered). Three (3) additional patients will be entered at the next lowest dose level if only 3 patients were treated previously at that dose.

1 out of 3	Enter at least 3 more patients at this dose level. 

• If 0 of these 3 patients experience DLT, proceed to the next dose level.

• If 1 or more of this group suffer DLT, then dose escalation is stopped, and this dose is declared the maximally administered dose. Three (3) additional patients will be entered at the next lowest dose level if only 3 patients were treated previously at that dose.

≤1 out of 6 at highest dose level	This is generally the maximum tolerated dose, MTD. At least 6 patients must be entered at the MTD.

### 5.3 **Dose Expansion Cohorts:**

A total of 15 patients will be treated at the MTD (including the 6 from dose expansion) to assess safety and feasibility of this dose level. The MTD will be deemed to be recommended phase II dose (RP2D) if  $\geq 80\%$  of the patients are able to receive  $\geq 80\%$  of the planned treatment doses. If  $\geq 1/3$  of all patients at this dose experience DLTs, enrollment will be stopped and the Principal Investigator will discuss with all study investigators and with CTEP whether further addition of patients is needed to re-assess the RP2D. Monitoring of all safety and toxicity data is done by the Principal Investigator and the Corresponding Organization on a real-time basis as data are entered into Medidata Rave using the Web Reporting Module.

### 5.4 **General Concomitant Medication and Supportive Care Guidelines**

5.4.1 Talamogene laherparepvec is sensitive to acyclovir and other antiherpetic viral drugs, and would be rendered ineffective. Thus, if systemic anti-herpetic medication is indicated, talamogene laherparepvec should be discontinued.

5.4.2 Where to locate information:

- For “Instructions for talamogene laherparepvec Injection Site Care”, refer to Section 5.1.1.2
- For “Information Related to Exposure to talamogene laherparepvec”, refer to 5.1.1.3, Appendices C1, C2
- For Information Sheet for Patient, Close Contacts and Non-study HCP, please refer to Appendix C. This Information should be provided to the care giver, family members, and close contacts of patients receiving talamogene laherparepvec on this trial

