## 6. DOSING DELAYS/DOSE MODIFICATIONS

### 6.1 Talimogene Laherparepvec Dose Delay and Treatment Discontinuation Guidelines

## **AEs that are considered “Dose Limiting” for talimogene laherparepvec Treatment**

### **Modification Guidelines**

- 1) **Herpetic events** that should be considered DLTs:
  - a. Serious herpetic events such as herpetic encephalitis, encephalomyelitis or disseminated herpetic infection
  - b. Any herpetic events confirmed due to talimogene laherparepvec that require treatment with acyclovir or similar anti-viral agent. Talimogene laherparepvec treatment should be held if systemic acyclovir or other anti-viral is indicated. If ongoing anti-viral treatment is required, talimogene laherparepvec treatment should be permanently discontinued
- \*Herpetic events due to wild-type HSV-1 or wild-type HSV-2 which require acyclovir and are not due to talimogene laherparepvec (as confirmed by PCR testing) should not be considered as DLTs caused by talimogene laherparepvec.
- 2) A DLT will also be defined as any of the following talimogene laherparepvec-related toxicity
  - o Grade 2 or greater immune-mediated AEs.
  - o Grade 2 or greater allergic reactions.
  - o Any grade plasmacytoma
  - o Any other grade 3 or greater hematologic or non-hematologic toxicity, with the exceptions of:
    - any grade of alopecia,
    - grade 3 arthralgia or myalgia,
    - brief (< 1 week) grade 3 fatigue,
    - grade 3 fever,
    - grade 3 diarrhea or vomiting responding to supportive care.

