### **Dose Reductions/delay:**

- Dose reductions with regards to changes in the concentrations of talimogene laherparepvec are not permitted. However, patients may require a reduction in the volume injected due to a disease response (defined in dosing section) or due to local toxicity at the injection site.
- If talimogene laherparepvec treatment was delayed due to AEs or other reasons by >1 week, that dose will be deemed to have been missed and the subject will proceed to the next scheduled treatment visit.
- If DLTs occur, talimogene laherparepvec administration should be delayed until the DLT has resolved to at least CTCAE version 5.0 Grade 1. (AEs less than DLT may also require talimogene laherparepvec dose delay. See instructions in Table below)
- If talimogene laherparepvec dosing is delayed by more than 4 weeks (approximately 6 weeks from the previous dose) due to treatment related AEs, talimogene laherparepvec should be permanently discontinued.
- If talimogene laherparepvec dosing is delayed by more than 4 weeks (approximately 6 weeks from the previous dose) for reasons other than treatment-related toxicity, the case

must be reviewed by the sponsor of the study (CTEP) to determine if the subject can resume talimogene laherparepvec therapy.

Treatment delays and discontinuation due to Specific AEs		
Condition	Grade	talimogene laherparepvec modification
• Injection site reactions		Volume of talimogene laherparepvec injection may be adjusted and should be held based on the degree of local toxicities
• Active herpetic cutaneous or mucosal lesions, herpes labialis, or active dermatosis in the region of the injected tumor (s)		Mild: continue talimogene laherparepvec; If requiring systemic acyclovir or similar anti-viral agents: Hold talimogene laherparepvec.
• Serious herpetic events such as herpetic encephalitis, encephalomyelitis or disseminated herpetic infection	Any grade	Discontinue talimogene laherparepvec
• Any condition requiring corticosteroid dosing of >10 mg prednisone daily (or equivalent) and/or other immunosuppressive medication for related toxicities	N/A	Hold talimogene laherparepvec dosing until corticosteroid dose has decreased to <10 mg prednisone daily (or equivalent) and the other immunosuppressive medication has been stopped.
• Plasmacytoma	Any grade	Permanently discontinue talimogene laherparepvec

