## 6.2 Other Agent(s)

*Dose modification guidelines for talimogene laherparepvec are listed in Section 6.1.*

Event Name	Oxaliplatin Neuropathy		
	Duration of Toxicity		
Grade of Event	1-7 days	>7 days	Persistent between cycles
Grade 1 Paresthesias/dysesthesias b that do not interfere with function	No change in dose	No change in dose	No change
Grade 2 Paresthesias/dysesthesias b interfering with function, but not activities of daily living (ADL)	No change in dose	No change in dose	Decrease by 1 dose level
Grade 3 Paresthesias/dysesthesias b with pain or with functional impairment that also interfere with ADL	No change	Decrease by 1 dose level	Stop oxaliplatin
Grade 4 Persistent paresthesias/dysesthesias that are disabling or life- threatening	Stop oxaliplatin	Stop oxaliplatin	Stop oxaliplatin
Laryngopharyngeal dysesthesia	↑ duration of next infusion to 6 hours c		

a Not resolved by the beginning of the next cycle.

b May be cold induced.

Event Name	Oxaliplatin hypersensitivity
Grade of Event	Management/Next Dose for Oxaliplatin
≤ Grade 1	Premedications with antihistamines, steroids and slow rate of oxaliplatin by half with future doses
Grade 2	Premedications with antihistamines, steroids and slow rate of oxaliplatin by half with future doses or discontinue oxaliplatin per discretion of treating physician
Grade 3	Discontinue oxaliplatin
Grade 4	Discontinue oxaliplatin
*Patients requiring a delay of >2 weeks should go off protocol therapy.	

Event Name	Hand Foot Syndrome	
	Management/Next Dose for Oxaliplatin	Management/Next Dose for 5-FU
≤ Grade 1	No change in dose	No change in dose
Grade 2	No change in dose	No change in dose
Grade 3	Hold all treatment until recovery ≤ grade 1 but may continue radiation if deemed safe by investigators; No change in dose	Hold all treatment until recovery ≤ grade 1 but may continue radiation if deemed safe by investigators; No change in dose
Grade 4	Off protocol therapy	Off protocol therapy
*Patients requiring a delay of >2 weeks should go off protocol therapy.		

Event Name	Vomiting	
	Management/Next Dose for Oxaliplatin	Management/Next Dose for 5-FU
≤ Grade 1	No change in dose	No change in dose
Grade 2	Hold until ≤ Grade 1. Resume at same dose level.	Hold until ≤ Grade 1. Resume at same dose level.

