### 13.4 Analysis of Secondary Endpoints

Secondary objectives of the study include determining feasibility and NAR.. Feasibility will be reported in all patients who have started therapy as percent of planned dose intensity, NAR will be reported in all patients who undergo resection. NAR will be calculated as detailed in section 2.6 and will be reported using descriptive statistics. pCR will be reported with proportions along with the appropriate confidence intervals and survival by Kaplan-Meier method. Descriptive statistics will be used to report results of other correlative studies discussed above. Tumors will

be characterized into good and poor responders to enable binary comparison. mrTRG is based on similar principles to the pathologic TRG and is based on the degree of tumor replaced by fibrotic stroma on post-treatment pelvic MRI. mrTRG-5 (no fibrosis, only tumor signal visible), mrTRG4 (predominantly tumor signal with minimal fibrotic stroma) will be defined as poor responders whereas mrTRG-1 (no tumor signal) to mrTRG-3 (50% or greater fibrotic stroma) will be defined as good. For the purposes of CRM, a margin greater than or equal to 1 mm between the tumor and the resection margin will be defined as clear (good responder) and the rest as poor responders. Prognosis of good responders including DFS, OS and local recurrence will be compared to that of poor responders. Furthermore, mrTRG will be compared to histological TRG (ypTRG) to validate its accuracy. Two radiologists with extensive experience with rectal MRIs (Drs. [name] & [name]) will read all the scans to minimize inter-observer variability.

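### Section 5.4.1 stops talimogene laherparepvec when a systemic antiviral is indicated, while Sections 5.2 and 6.1 only hold it for a time-limited course

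*Combined protocol and SAP*

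**What the plan says.** Section 5.4.1, on concomitant medication, describes the agent as "sensitive to acyclovir and other antiherpetic viral drugs, and would be rendered ineffective" and concludes that "if systemic anti-herpetic medication is indicated, talamogene laherparepvec should be discontinued". It makes no exception for a short course and says nothing about resuming.

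Sections 5.2 and 6.1 list the dose-limiting herpetic events and share the same wording: "Talimogene laherparepvec treatment should be held if systemic acyclovir or other anti-viral is indicated". They add: "If ongoing anti-viral treatment is required, talimogene laherparepvec treatment should be permanently discontinued".

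The table of delays and discontinuations in Section 6.1 has a row for active herpetic lesions, including herpes labialis. Mild cases continue treatment, and for the rest the row says: "If requiring systemic acyclovir or similar anti-viral agents: Hold talimogene laherparepvec". A separate row discontinues the agent for serious herpetic events of any grade.

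Section 6.1 also says that when an injection is delayed by more than one week, "that dose will be deemed to have been missed and the subject will proceed to the next scheduled treatment visit". A delay of more than four weeks from a treatment-related adverse event ends talimogene permanently. A delay of that length for another reason goes to CTEP for review.

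For the analysis, Section 13.4 states: "Feasibility will be reported in all patients who have started therapy as percent of planned dose intensity". Sections 5.3 and 13.1 make the MTD the RP2D if at least 80% of patients can receive at least 80% of planned treatment doses.

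**The concern.** The trigger is the same in every place: a systemic antiviral is indicated. The action is not. Section 6.1 uses hold and discontinue as separate steps, so a reader who applies that vocabulary to Section 5.4.1 will stop the agent for good. A reader who starts from Section 5.2 or 6.1 will pause and resume. The two cannot both be followed for a non-serious event treated with a time-limited course.

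At stake are the number of injections a patient receives, the dose intensity reported as the feasibility result and, in some cases, whether that patient meets the 80% criterion in the RP2D rule. In a trial of at most 21 patients (Section 13.2), identical events handled differently would blur a secondary endpoint and alter individual treatment for no clinical reason.

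**Working it through.** **Instructions side by side**

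| Situation | Section 5.4.1 | Sections 5.2 and 6.1 | Agree? |
|---|---|---|---|
| Serious herpetic event | Discontinue | Discontinue (6.1 table) | Yes |
| Ongoing systemic antiviral needed | Discontinue | Permanently discontinue | Yes |
| Non-serious event, time-limited systemic course | Discontinue | Hold | No |

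For events confirmed as due to talimogene, the hold appears in the text of Sections 5.2 and 6.1 and in the table. For wild-type HSV it rests on the table row alone, which does not distinguish the source of the virus.

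**Injections received.** Section 5.1 places injections at weeks 0, 3, 5 and 7. An injection is lost only if delayed by more than one week.

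| Event after | Discontinued | Held, no dose lost | Held, one dose lost |
|---|---|---|---|
| Dose 1 | 1/4 = 25% | 4/4 = 100% | 3/4 = 75% |
| Dose 2 | 2/4 = 50% | 4/4 = 100% | 3/4 = 75% |
| Dose 3 | 3/4 = 75% | 4/4 = 100% | 3/4 = 75% |

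**80% criterion for one patient.** The plan does not define a planned treatment dose, so I took four readings and assumed that all chemotherapy and radiation are delivered. The counts come from Section 5.1: 4 injections, 8 FOLFOX doses and 5 fractions. That gives 4 + 8 + 5 = 17 doses, 4 + 8 + 1 = 13 with radiation counted once, 4 + 8 = 12 with radiation excluded, or talimogene alone.

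| Discontinued after | Doses lost | Of 17 | Of 13 | Of 12 |
|---|---|---|---|---|
| Dose 1 | 3 | 14/17 = 82.4% | 10/13 = 76.9% | 9/12 = 75.0% |
| Dose 2 | 2 | 15/17 = 88.2% | 11/13 = 84.6% | 10/12 = 83.3% |
| Dose 3 | 1 | 16/17 = 94.1% | 12/13 = 92.3% | 11/12 = 91.7% |

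- Of 17: never below 80%, so the choice of section does not change the patient's status.
- Of 13 or 12: discontinuing after dose 1 fails the criterion. A hold that costs at most two injections passes it (11/13 = 84.6%, 10/12 = 83.3%). Later events make no difference.
- Talimogene alone: discontinuing fails (25% to 75%). Holding passes only if no injection is lost, because 3/4 = 75%.

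**Frequency.** The documents give no rate of systemic antiviral use. The nearest figure, in Section 2.2.1.2.2, is 5.5% of talimogene-treated patients reporting oral or corneal herpes. Assuming that 20% to 50% of such cases need a systemic course, p = 0.055 × 0.20 = 0.011 to 0.055 × 0.50 = 0.0275.

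- At least one in 6 patients: 1 − (1 − p)^6 = 6.4% to 15.4%.
- At least one in 15 patients: 1 − (1 − p)^15 = 15.3% to 34.2%.

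Both ranges are too high for this purpose, because only events before the week 7 injection matter.

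**What does not change.** DLT classification does not depend on whether the agent is then held or stopped. Evaluability for escalation in Section 5.2 counts chemotherapy and radiation only. DLT counts and the MTD are therefore unaffected.

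**The case against.** The best defence is that the protocol already says where the rule lives. Sections 5.1, 5.2 and 5.5 point to Section 6 for modifications, and Section 6.2 states: "Dose modification guidelines for talimogene laherparepvec are listed in Section 6.1". A site that follows these pointers arrives at hold. This shows which text to keep, but no clause says that Section 6 overrides 5.4.1. Section 5.4 is also where staff would look when prescribing acyclovir, and its list of cross-references does not include Section 6.

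A second argument is that 5.4.1 omits the word permanently and gives a reason, loss of viral activity, that applies only while the antiviral is given. A temporary stop is a possible reading. It is not the natural one, because the Section 6.1 table uses discontinue without that qualifier for serious events, where a stop is meant.

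The points about size are fair:

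- Sections 3.2.9 and 3.2.10 exclude patients with active herpetic skin lesions, prior herpetic complications or viral infections needing systemic antiherpetics, so the event should be rarer than the ranges above.
- One patient's status seldom settles the RP2D rule: with 15 patients it needs 0.80 × 15 = 12, so three may fail.
- Suspected herpetic events are reported to CTEP as SAEs (Section 7.3.4), and at least monthly calls are planned (Section 12.1), so divergence between sites would probably be noticed.

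These points limit the consequence. They do not reconcile the text.

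**Conclusion.** The concern holds. For a non-serious herpetic event needing a time-limited systemic antiviral, Section 5.4.1 stops talimogene while Sections 5.2 and 6.1 hold it. Both prevent injection during the antiviral course, and they differ only on resumption.

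The difference for one patient is up to three of four injections. The effect on the 80% criterion ranges from none to a change of status, depending on an undefined denominator and on the assumption that the other planned doses are given. The frequency range rests on an assumed share of systemic use and should be read as an upper guide. The practical effect is small, but an operative dosing rule should have one version, so the text should be corrected.

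**What to change.** Amend Section 5.4.1 to match Section 6.1: hold talimogene while a systemic antiviral is given, and discontinue permanently if antiviral treatment is ongoing, if the event is a serious herpetic event, or if a treatment-related adverse event delays dosing by more than four weeks. A delay of that length for another reason goes to CTEP review, as Section 6.1 already provides. A cross-reference from 5.4.1 to Section 6.1 would help keep the two aligned.

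The cost is one sentence in an amendment. Every existing safety stop is kept, and design, sample size and data collection are unchanged.

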### 5.5 **Duration of Therapy**

In the absence of treatment delays due to adverse event(s), treatment may continue for *the*

duration of the therapy per protocol or until one of the following criteria applies:

- Disease progression
- Intercurrent illness that prevents further administration of treatment
- Unacceptable adverse event(s) Please refer to section 6 Treatment Modification Guidelines
- Patient decides to withdraw from the study
- General or specific changes in the patient's condition render the patient unacceptable for further treatment in the judgment of the investigator
- Clinical progression
- Patient non-compliance
- Pregnancy
  - All women of child bearing potential should be instructed to contact the investigator immediately if they suspect they might be pregnant (e.g., missed or late menstrual period) at any time during study participation.
  - The investigator must immediately notify CTEP in the event of a confirmed pregnancy in a patient participating in the study.
- Termination of the study by sponsor
- The drug manufacturer can no longer provide the study agent

The reason(s) for protocol therapy discontinuation, the reason(s) for study removal, and the corresponding dates must be documented in the Case Report Form (CRF).

## 5.6 Duration of Follow Up

Patients will be followed for 30 days after removal from study or until death, whichever occurs first. Patients who have undergone curative resection will be monitored for a minimum of 2 years (and up to 5 years) for disease recurrence. Patients removed from study for unacceptable adverse event(s) will be followed until resolution or stabilization of the adverse event.

## 6. DOSING DELAYS/DOSE MODIFICATIONS

### 6.1 Talimogene Laherparepvec Dose Delay and Treatment Discontinuation Guidelines

## **AEs that are considered “Dose Limiting” for talimogene laherparepvec Treatment**

### **Modification Guidelines**

- 1) **Herpetic events** that should be considered DLTs:
  - a. Serious herpetic events such as herpetic encephalitis, encephalomyelitis or disseminated herpetic infection
  - b. Any herpetic events confirmed due to talimogene laherparepvec that require treatment with acyclovir or similar anti-viral agent. Talimogene laherparepvec treatment should be held if systemic acyclovir or other anti-viral is indicated. If ongoing anti-viral treatment is required, talimogene laherparepvec treatment should be permanently discontinued
- \*Herpetic events due to wild-type HSV-1 or wild-type HSV-2 which require acyclovir and are not due to talimogene laherparepvec (as confirmed by PCR testing) should not be considered as DLTs caused by talimogene laherparepvec.
- 2) A DLT will also be defined as any of the following talimogene laherparepvec-related toxicity
  - o Grade 2 or greater immune-mediated AEs.
  - o Grade 2 or greater allergic reactions.
  - o Any grade plasmacytoma
  - o Any other grade 3 or greater hematologic or non-hematologic toxicity, with the exceptions of:
    - any grade of alopecia,
    - grade 3 arthralgia or myalgia,
    - brief (< 1 week) grade 3 fatigue,
    - grade 3 fever,
    - grade 3 diarrhea or vomiting responding to supportive care.

### **Dose Reductions/delay:**

- Dose reductions with regards to changes in the concentrations of talimogene laherparepvec are not permitted. However, patients may require a reduction in the volume injected due to a disease response (defined in dosing section) or due to local toxicity at the injection site.
- If talimogene laherparepvec treatment was delayed due to AEs or other reasons by >1 week, that dose will be deemed to have been missed and the subject will proceed to the next scheduled treatment visit.
- If DLTs occur, talimogene laherparepvec administration should be delayed until the DLT has resolved to at least CTCAE version 5.0 Grade 1. (AEs less than DLT may also require talimogene laherparepvec dose delay. See instructions in Table below)
- If talimogene laherparepvec dosing is delayed by more than 4 weeks (approximately 6 weeks from the previous dose) due to treatment related AEs, talimogene laherparepvec should be permanently discontinued.
- If talimogene laherparepvec dosing is delayed by more than 4 weeks (approximately 6 weeks from the previous dose) for reasons other than treatment-related toxicity, the case

must be reviewed by the sponsor of the study (CTEP) to determine if the subject can resume talimogene laherparepvec therapy.

Treatment delays and discontinuation due to Specific AEs		
Condition	Grade	talimogene laherparepvec modification
• Injection site reactions		Volume of talimogene laherparepvec injection may be adjusted and should be held based on the degree of local toxicities
• Active herpetic cutaneous or mucosal lesions, herpes labialis, or active dermatosis in the region of the injected tumor (s)		Mild: continue talimogene laherparepvec; If requiring systemic acyclovir or similar anti-viral agents: Hold talimogene laherparepvec.
• Serious herpetic events such as herpetic encephalitis, encephalomyelitis or disseminated herpetic infection	Any grade	Discontinue talimogene laherparepvec
• Any condition requiring corticosteroid dosing of >10 mg prednisone daily (or equivalent) and/or other immunosuppressive medication for related toxicities	N/A	Hold talimogene laherparepvec dosing until corticosteroid dose has decreased to <10 mg prednisone daily (or equivalent) and the other immunosuppressive medication has been stopped.
• Plasmacytoma	Any grade	Permanently discontinue talimogene laherparepvec
• Immune-mediated AEs (These may include pauci-immune glomerulonephritis, vasculitis, and pneumonitis, but may involve any organ system)	Grade 2 or greater	Hold talimogene laherparepvec (with the exception of vitiligo). If delay is > 4 weeks, discontinue talimogene laherparepvec
• Allergic reactions, or urticaria	Grade 2 or greater	Hold talimogene laherparepvec. If delay is > 4 weeks, permanently discontinue talimogene laherparepvec

 
• Other talimogene laherparepvec related grade 3+ AEs or intolerable grade 2 AEs (Except brief grade 3 fever, fatigue, pain, or nausea/vomiting responding to supportive care)
 
		
Hold talimogene laherparepvec until AE is grade 0-1.
 
 
• If delay is > 4 weeks, discontinue talimogene laherparepvec
 
• If the AE was grade 4, decision to resume talimogene laherparepvec upon recovery should be reviewed with the sponsor (CTEP)
 

--	--	---

